Standard descriptive statistics (proportions and frequencies for categorical factors; means, standard deviations, and designated percentiles for numeric factors) will display baseline characteristics by randomized treatment group. If a substantial imbalance is identified in a particular baseline factor, the ITT analyses described below will be accompanied by sensitivity analyses to investigate the impact of inclusion of this factor as a covariate. Outcomes with substantial skewness may be transformed prior to subsequent analyses to better approximate normality. Analyses evaluating the effect of the treatment on study outcomes will be performed in accordance with the intention-to-treat principle, with subjects analyzed according to their randomly assigned treatment irrespective of the achieved dose of Vericiguat. Unless specified otherwise, hypothesis tests will be performed with 2-sided α =0.05, without adjustment for multiple comparisons.

Primary Analysis

The effect of administration of Vericiguat on the primary FMD outcome will be estimated by applying an analysis of covariance to compare the mean FMD levels at 12 weeks between the Vericiguat and placebo groups, with the baseline FMD levels included in the model as a covariate.

Secondary Analyses

The effect of administration of Vericiguat on the secondary 6-minute walk test and KCCQ outcomes will be estimated by applying separate analyses of covariance to compare the mean levels of these outcomes at 12 weeks between the Vericiguat and placebo groups, with the baseline level of the outcome included as a covariate. Separate analysis of covariance models will also be used to estimate the effects of the intervention on C-Reactive Protein and Interleukinç 1β , 6, 18. If these markers exhibit heavy positive skewness, as we expect, they will be log transformed prior to analysis.

We will also provide scatter plots with Pearson and Spearman partial correlations with adjustment for randomized treatment group to describe the association of the change in FMD from baseline to 12 weeks with changes in individual inflammatory markers during the same time interval. We will also provide Pearson and Spearman correlations relating changes in FMD to changes in inflammatory markers separately within the two randomized groups. Positively skewed inflammatory markers will be log transformed prior to this analysis.

Power analyses

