We expect to enroll and randomize 24 study subjects. With an anticipated drop-out rate of 15%, data from 20 subjects will be available for analysis.

Primary Outcome.

Flow-Mediated Dilation (FMD): Output from FMD testing is maximal change in brachial artery diameter across a 2-min period following 5 min of supra-systolic arterial occlusion, expressed as % change from pre-occlusion baseline. We hypothesize that the treatment will lead to a 5.1% increase in FMD relative to the control group. We anticipate a standard deviation (SD) in %FMD 2.4% in patients with HFrEF. With this SD, 10 evaluable patients per treatment group will provide at least 80% power with 2-sided α =0.05 to detect an increase in mean %FMD of 3.18% relative to the control group. The minimum detectable effect of 3.18% is well under the hypothesized effect size of 5.1%, indicating that the design has excellent statistical power to evaluate the hypothesized treatment effect on the primary outcome. This power calculation conservatively assumes a 0 correlation between the baseline and 12-week FMD values; if the serial correlation is at least 0.5, the study will have at least 80% power to detect an 2.76% increase in %FMD.

Secondary Outcomes

6MWT: We anticipate SD of 100 m in the 6MWT. With this assumed SD, 10 evaluable patients per treatment group will provide at least 80% power with 2-sided α =0.05 to detect an increase in 6MWT distance of 115 m so long as the serial correlation between the baseline and 12 week 6MWT values is at least 0.5.

Kansas City Cardiomyopathy Questionnaire (KCCQ): We anticipate an SD for the change in the KCCQ of 19.9 points. Based on this assumed SD, 10 evaluable patients per treatment group will provide at least 80% power with 2-sided α =0.05 to detect an improvement in mean KCCQ of 24.4 points. It is anticipated that KCCQ score changes will be smaller. The absolute differences may be hypothesis generating and provide pilot data for future targeted investigations.

hsCRP: We project a median and interquartile range from the baseline hsCRP values of 3.68 mg/L and (1.14-8.41 mg/L), respectively. Under the assumption that hsCRP is lognormally distributed, we estimate an SD of 1.323 for log transformed hsCRP. Based on this assumed SD, 10 evaluable patients per treatment group will provide at least 80% power with 2-sided α =0.05 to detect an 83% reduction in the geometric mean hsCRP for the treatment group compared to the control group.

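### The 80% power figures for FMD and 6MWT leave out the cost of the baseline covariate; the planned ANCOVA has about 77–78% power at the stated effects with 10 per arm

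*Combined protocol and SAP*

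**What the plan says.** Under Primary Analysis, the combined protocol and SAP plans an "analysis of covariance to compare the mean FMD levels at 12 weeks between the Vericiguat and placebo groups", with baseline FMD as covariate. Secondary Analyses plans the same model for 6MWT. The General paragraph sets the error rate: "hypothesis tests will be performed with 2-sided α =0.05, without adjustment for multiple comparisons".

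Under Power analyses, the claim for each outcome is that "10 evaluable patients per treatment group will provide at least 80% power":

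- FMD, SD 2.4: 3.18 points. The section adds: "This power calculation conservatively assumes a 0 correlation between the baseline and 12-week FMD values".
- FMD, correlation of 0.5 or more: "the study will have at least 80% power to detect an 2.76% increase in %FMD".
- 6MWT, SD 100 m: the claim is power "to detect an increase in 6MWT distance of 115 m so long as the serial correlation" is 0.5 or more.

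The section does not name the power formula. Its main argument is that 3.18 points lies well below the hypothesised 5.1 points.

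**The concern.** The power section sets a floor of 80% for a trial whose named analysis is ANCOVA. With 20 patients, adjusting for baseline has two costs: one error degree of freedom, and extra variance because the slope is estimated and the arms differ at baseline by chance. Both are negligible in a large trial, but the second is not negligible here. If the figures come from a formula that ignores these costs, the planned model does not reach the stated floor at the stated inputs. What is at stake is the accuracy of the quoted minimum detectable effects, and the use a reader may make of them when planning a later study.

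**Working it through.** **Inputs.** From Power analyses: 10 evaluable per group; SD 2.4 points (FMD) and 100 m (6MWT); correlations 0 and 0.5; effects 3.18, 2.76 and 115 m; hypothesised FMD effect 5.1 points. From General: two-sided α = 0.05. From Primary and Secondary Analyses: ANCOVA with one baseline covariate. I read the SDs as those of the 12-week value, equal in both arms, and take outcome and baseline as normal.

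**Step 1: reproduce the plan's figures.** For a two-sample t-test, df = 18 and the noncentrality is Δ / (SD·√(2/10)). Power of 80% needs Δ/SD = 1.32495. For r = 0.5, multiply the SD by √(1 − 0.5²) = 0.8660.

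- FMD, r = 0: 1.32495 × 2.4 = 3.180 (stated 3.18; power 80.0%)
- FMD, r = 0.5: 1.32495 × 2.4 × 0.8660 = 2.754 (stated 2.76; power 80.2%)
- 6MWT, r = 0.5: 1.32495 × 100 × 0.8660 = 114.7 m (stated 115 m; power 80.2%)

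The normal approximation gives 3.01 for the first figure, so it is not the source.

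**Step 2: the planned ANCOVA.** Error df = 20 − 3 = 17. The variance of the adjusted difference is SD²·(1 − r²)·(2/10)·V. For a normal baseline in a randomised trial, V = 1 + χ²(1)/χ²(18), with mean 1 + 1/16 = 1.0625. Given V, power follows a noncentral t with 17 df and noncentrality Δ / (SD·√(1 − r²)·√(0.2·V)). I average this over V.

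| Stated effect | t-test, 18 df | 17 df only (V = 1) | ANCOVA, averaged over V | Simulated ANCOVA (200,000 trials) | Effect with 80% power |
|---|---|---|---|---|---|
| FMD 3.18, r = 0 | 80.0% | 79.7% | 77.4% | 77.4% | 3.29 |
| FMD 2.76, r = 0.5 | 80.2% | 79.9% | 77.6% | 77.5% | 2.85 |
| 6MWT 115 m, r = 0.5 | 80.2% | 79.9% | 77.6% | 77.5% | 118.6 m |

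Nearly all of the loss comes from V. The detectable effect rises by 3.286/3.180 = 1.033, about 3%.

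**Step 3: dependence on the correlation.** ANCOVA power at 3.18 points is 77.4% at r = 0, 79.0% at 0.2, 81.1% at 0.3, 84.0% at 0.4 and 87.8% at 0.5. It reaches 80% at r ≈ 0.25. For 2.76 points and 115 m, 80% is reached at r ≈ 0.54.

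**Step 4: the hypothesised effect.** ANCOVA power at 5.1 points is 99.0% at r = 0 and 99.9% at r = 0.5.

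**The case against.** Applying only the √(1 − r²) discount is a common planning approximation, and the plan does not claim an exact ANCOVA calculation. The correction is smaller than the uncertainty in the SD: lowering 2.4 to 2.32 (3.18 / 1.3695) restores 80% at r = 0. If the arms happen to be balanced at baseline, power is 79.7% to 79.9%. The 6MWT analysis is declared exploratory. All of this stands and keeps the point minor. It does not make a stated floor of 80% correct for the named model at the stated inputs.

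Three stronger readings are tempting, and the documents do not support them.

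- *The word conservative is wrong.* The plan attaches it to the choice of zero correlation. Zero is the worst case for ANCOVA, because residual variance is largest there, and power at 3.18 points rises with the correlation. What fails is narrower: zero correlation does not by itself make 3.18 points a guaranteed 80% effect for the planned model. The documents give no estimate of the FMD correlation (0.5 appears only as a scenario), so nobody can say from them whether the true value is above or below 0.25.
- *The trial is too small for its primary question.* At 5.1 points power is about 99% even at r = 0, and 3.29 is still well under 5.1.
- *Unequal drop-out breaks the claim.* If the 20 completers split 9/11 or 8/12, ANCOVA power at 3.18 points is 77.0% or 75.7%. But the claim is conditioned on 10 evaluable patients in each group, so these splits do not contradict it. The documents state neither the allocation ratio nor that drop-outs are independent.

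The enrolment figure is a separate matter. Power analyses says "We expect to enroll and randomize 24 study subjects", while Study Population gives 30. With 11 evaluable per arm, ANCOVA power is about 82% at all three effects, so more evaluable patients would remove the shortfall. The two enrolment figures need reconciling, but the power claim as written rests on 10 per arm.

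**Conclusion.** The point holds as a minor correction. The three power statements belong to a t-test with a large-sample discount. At the same inputs the planned ANCOVA falls about 2.5 percentage points short of the 80% floor. The shortfall applies when the absolute correlation is below about 0.25 for 3.18 points, and when it lies between 0.5 and about 0.54 for 2.76 points and 115 m; above those values the statements are true. The result rests on 10 evaluable patients per arm, the plan's own SDs, and normal outcome and baseline values. The sample size, and the plan's conclusion about the 5.1-point effect, are unaffected.

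**What to change.** In Power analyses, do one of the following:

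1. State the effects detectable with 80% power under the planned ANCOVA: about 3.29 points of FMD at r = 0, 2.85 points at r = 0.5, and 119 m of 6MWT at r = 0.5.
2. Keep 3.18 points, 2.76 points and 115 m, and give the power as about 77–78%.

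In either case, name the method (ANCOVA, 17 df, averaged over chance baseline imbalance). Keep zero correlation as the cautious input. If option 2 is chosen, add that 80% is reached at 3.18 points only from a correlation of about 0.25, and at 2.76 points and 115 m from about 0.54. Values for 9/11 and 8/12 splits would be informative but are optional.

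The cost is a few sentences. No patients, procedures or analyses change, and the quoted effects become about 3% less favourable.

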Interleukins 1 β , 6, 18 and TNF- α : We also assume an SD of 1.323 for log transformed IL-1 β , IL-6, IL-18, TNF- α . Hence, we also expect that 10 evaluable patients per treatment group will provide at least 80% power with 2-sided α =0.05 to detect an 83% reduction in the geometric mean of these biomarkers for the treatment group compared to the control group.

We note that with 10 patients per group, our proposed design provides excellent statistical power to detect the hypothesized treatment effect on the primary outcome of FMD. Our statistical power will allow to detect large effects on the secondary outcomes. Hence, analyses of the secondary outcomes will be exploratory.

Correlational analyses

A sample size of 20 evaluable subjects is sufficient to detect a partial correlation of 0.59 with 80% power and 2-sided type-1 error of 5%.

Multiplicity. In this preliminary study, all hypothesis tests will be performed on a comparisonwise basis, without adjustment for multiple comparisons.

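### The KCCQ detectable difference of 24.4 points does not follow from the stated SD of change of 19.9, which gives 26.4; under the planned ANCOVA it needs a correlation the plan does not state

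*Combined protocol and SAP*

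**What the plan says.** In Power analyses, Secondary Outcomes, the KCCQ paragraph gives one variance input: "We anticipate an SD for the change in the KCCQ of 19.9 points". From that SD it states that 10 evaluable patients per group have at least 80% power at two-sided 0.05 "to detect an improvement in mean KCCQ of 24.4 points". It adds no other condition, and then remarks: "It is anticipated that KCCQ score changes will be smaller".

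The neighbouring paragraphs state what their figures depend on. For FMD: "This power calculation conservatively assumes a 0 correlation between the baseline and 12-week FMD values", followed by a second figure at a correlation of 0.5. For 6MWT, the 115 m figure holds "so long as the serial correlation between the baseline and 12 week 6MWT values is at least 0.5". The hsCRP paragraph, like KCCQ, cites only an SD, and claims 80% power "to detect an 83% reduction in the geometric mean hsCRP for the treatment group".

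Under Secondary Analyses, KCCQ is to be analysed by ANCOVA of the 12-week level, "with the baseline level of the outcome included as a covariate". The closing note on secondary outcomes says: "Hence, analyses of the secondary outcomes will be exploratory".

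**The concern.** Read as written, the KCCQ sentence is a complete calculation: an SD of change, 10 per group, two-sided 0.05 and 80% power lead to 24.4 points. They do not. If the figure instead comes from the planned ANCOVA, it depends on a baseline to 12-week correlation that is given for FMD and 6MWT but not for KCCQ.

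The direction of that dependence is easy to get wrong. For FMD and 6MWT the SD is that of the measurement, so a higher correlation helps and a lower limit is the right condition. For KCCQ the SD is that of the change. With that SD held fixed, a higher correlation means a larger ANCOVA residual SD and less power, so the condition must be an upper limit. A reader who carries the 6MWT wording over to KCCQ would have it backwards.

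At stake is whether a reader can reproduce the figure and tell when 80% power holds. The plan suggests the KCCQ differences may serve as pilot data for later studies, so the basis of the figure should be clear.

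**Working it through.** **Inputs from the plan.** 10 evaluable per group; two-sided 0.05; 80% power; SD of KCCQ change 19.9; SD of %FMD 2.4; SD of 6MWT 100 m; SD of log hsCRP 1.323.

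**Method.** Noncentral t. The detectable difference is d × SD, with d = 1.3249 on 18 df (two-sample t-test) and d = 1.3295 on 17 df (one covariate). For an outcome with a per-visit SD, the ANCOVA residual SD is SD × √(1 − r²).

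**The plan's other figures are reproduced.**
- FMD, r = 0: 2.4 × 1.3249 = 3.18%.
- FMD, r = 0.5: 2.4 × √0.75 × 1.3295 = 2.76%.
- 6MWT, r = 0.5: 100 × √0.75 × 1.3295 = 115.1 m.
- hsCRP: 1 − exp(−1.323 × 1.3249) = 82.7%, stated as 83%.

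**KCCQ on its stated inputs.**
- 19.9 × 1.3249 = 26.37 points.
- Power at 24.4 is 73.7%.
- 24.4 would need an SD of 24.4 / 1.3249 = 18.4.
- The multiplier implied by 24.4 is 24.4 / 19.9 = 1.226. In the hsCRP line it would give 1 − exp(−1.323 × 1.226) = 80%, not 83%.
- A normal approximation does not explain the figure. It gives 24.9 for KCCQ, and 3.01 for FMD where the plan has 3.18.

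**KCCQ under the planned ANCOVA.** Assume equal SDs at the two visits. The per-visit SD is then 19.9 / √(2(1 − r)). Multiplying by √(1 − r²) gives a residual SD of 19.9 × √((1 + r)/2). The simple columns multiply this by 1.3295, as the plan's 2.76% and 115 m do. The last two columns also count chance baseline imbalance, by averaging power over a variance factor of (2/n)(1 + T²/18), with T distributed as t on 18 df.

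| r (assumed) | Detectable, simple | Power at 24.4, simple | Detectable, imbalance counted | Power at 24.4, imbalance counted |
|---|---|---|---|---|
| 0.5 | 22.9 | 84.7% | 23.6 | 82.5% |
| 0.6 | 23.7 | 82.3% | 24.4 | 80.1% |
| 0.7 | 24.4 | 80.0% | 25.1 | 77.7% |
| 0.8 | 25.1 | 77.7% | 25.9 | 75.4% |
| 0.9 | 25.8 | 75.5% | 26.6 | 73.1% |

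The 24.4 figure keeps 80% power up to r = 0.70 by the simple formula, and up to r = 0.60 with imbalance counted.

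**Unequal variances.** If the 12-week SD is k times the baseline SD, the residual SD is 19.9 × k√(1 − r²) / √(1 + k² − 2kr). At r = 0.5 with imbalance counted:
- k = 1.2: residual SD 18.57, power at 24.4 is 76.7%.
- k = 0.8: residual SD 15.04, power at 24.4 is 91.2%.

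The documents give no r and no SD ratio for KCCQ; every value used here is an assumption.

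**The case against.** The strongest reply is that the plan never proposes an unadjusted test of change for KCCQ. It proposes ANCOVA, and for ANCOVA the claim can be true: with equal variances and r = 0.5, the value used for FMD and 6MWT, power at 24.4 is 84.7% by the plan's own formula. On this view the sentence lacks an input but is not wrong. This stands in part: 24.4 is not an impossible figure. But the sentence derives it from the SD alone and attaches no condition. Nor can the reader fill the gap from the next paragraph, since r = 0.5 gives 22.9.

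A second reply is that counting chance imbalance is stricter than the plan is for any outcome. That is fair. On the same basis the plan's 115 m and 2.76% have 77.6% power, so the limit of 0.70, not 0.60, is the like-for-like comparison. The point holds on either.

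Third, the source of 24.4 is a guess. This also stands: r = 0.70 is back-solved and appears nowhere in the plan. An unadjusted test with 11 and 12 patients also gives 24.4, although that contradicts the stated 10 per group.

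Finally, little depends on the figure. The plan already expects smaller KCCQ changes and treats the secondary analyses as exploratory. This stands, and it keeps the point minor.

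**Conclusion.** The concern holds. As written, the claim of at least 80% power at 24.4 points does not follow from its stated inputs. They give 26.4 points, which is 2.0 points or 8% higher, and 73.7% power at 24.4. This rests only on the plan's numbers and on the method that reproduces its other detectable differences.

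Under the planned ANCOVA the claim is conditional: true at r = 0.5 with equal variances, and false above r of about 0.70 (about 0.60 with chance imbalance counted). It is also sensitive to the ratio of the two visits' SDs. These ANCOVA results rest on assumed correlations and variances. Sample size, analysis and the plan's own reading of KCCQ as underpowered for the expected change are unaffected.

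**What to change.** Either of two edits to the KCCQ paragraph would do.

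1. Restate the figure as about 26.4 points and label it as the unadjusted comparison of change. With equal variances and imbalance counted, this also covers the planned ANCOVA up to r of about 0.88. If one figure is wanted for ANCOVA at any correlation and SD ratio, about 27.3 points serves, because the residual SD cannot exceed the SD of the change (the limit at residual SD 19.9 is 27.2, rounded up).
2. Keep 24.4, and state that it is an ANCOVA figure, that equal variances are assumed, and that it holds for a correlation up to about 0.70 by the formula used for the other outcomes (about 0.60 with chance imbalance counted). The condition must be an upper limit.

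The first is simpler, because it needs no assumption the plan does not already make. The cost is one number or one clause, with no change to sample size, analysis or conduct.

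### The hsCRP quartiles (1.14 and 8.41 mg/L) give a log-scale SD of 1.48 under the plan's lognormal assumption, not the stated 1.323 on which the 83% detectable reduction rests

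*Combined protocol and SAP*

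**What the plan says.** All the inputs are in the hsCRP paragraph of Power analyses, Secondary Outcomes. The plan states: "We project a median and interquartile range from the baseline hsCRP values of 3.68 mg/L and (1.14-8.41 mg/L), respectively". It then assumes lognormality and continues: "we estimate an SD of 1.323 for log transformed hsCRP". From that SD, with 10 evaluable patients per group and a two-sided 5% level, it claims at least 80% power "to detect an 83% reduction in the geometric mean hsCRP for the treatment group compared to the control group".

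The paragraph gives no formula for the SD and no correlation between baseline and week 12. Elsewhere in the same section correlations are stated openly. For FMD the plan says: "This power calculation conservatively assumes a 0 correlation between the baseline and 12-week FMD values", and adds a second figure for a correlation of 0.5. For the 6MWT it assumes at least 0.5.

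The analysis itself is described under Secondary Analyses: "Separate analysis of covariance models will also be used to estimate the effects of the intervention on C-Reactive Protein". The next power paragraph carries the same value to the interleukins and TNF-α ("We also assume an SD of 1.323 for log transformed"). The section then concludes: "Hence, analyses of the secondary outcomes will be exploratory".

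**The concern.** For a lognormal variable, two quartiles determine the SD of the logged values, and the result here is not the SD the plan prints. Because the SD drives the power statement directly, a reader who starts from the printed quartiles cannot arrive at an 83% reduction with at least 80% power, and cannot tell whether that claim is true.

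What is at stake is one power statement, plus the matching statement for four other markers that use the same SD. The primary FMD calculation and the planned enrolment do not use it.

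**Working it through.** **Inputs (all from Power analyses).** Q1 = 1.14, median = 3.68, Q3 = 8.41 mg/L; lognormal distribution; stated log-scale SD 1.323; 10 per group; two-sided 0.05; 80% power; stated detectable reduction 83%.

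**Step 1: reproduce the plan's 83%.** For a two-sample t-test with 10 per group (18 degrees of freedom), the noncentral t gives a standardised difference of d = 1.325 at 80% power. As a check on the method, 1.325 × 2.4 = 3.18, which is the plan's FMD figure at zero correlation. For hsCRP, the reduction in geometric mean is

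1 − exp(−d × SD) = 1 − exp(−1.325 × 1.323) = 1 − exp(−1.753) = 82.7%.

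This rounds to the stated 83%. Power at exactly 83%, a log difference of ln(0.17) = −1.772, is 80.8% with SD 1.323. The step from SD to effect is correct.

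**Step 2: derive the SD from the quartiles.** Under lognormality the quartiles of log hsCRP lie 2 × 0.6745 = 1.349 SDs apart, so

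SD = ln(Q3/Q1)/1.349 = ln(8.41/1.14)/1.349 = 1.998/1.349 = 1.481.

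Rounding in the printed quartiles allows only 1.478 to 1.485. The stated 1.323 is about 11% lower. It would need Q3/Q1 = exp(1.323 × 1.349) = 5.96, whereas the printed ratio is 8.41/1.14 = 7.38. A least-squares fit on the log scale to all three values, median included, also gives 1.481.

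**Step 3: try other routes to 1.323.**

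| Route | SD |
|---|---|
| Q1 to median only | 1.737 |
| Median to Q3 only | 1.225 |
| Median with IQR width | 1.294 |
| Finite-sample quartile divisor (n = 20 to 1000) | 1.594 to 1.484 |
| log10 / log2 / log(1 + x) | 0.643 / 2.137 / 1.098 |
| Raw-scale SD converted through the CV | 0.956 to 1.070 |
| 1.481 with baseline correlation 0.5, × √(1 − 0.5²) | 1.283 |

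None gives 1.323. Two conjectures do:

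- *Misprinted quartile.* With Q1 = 1.41, ln(8.41/1.41)/1.35 = 1.323. The printed median fits this slightly better: a lognormal median is √(Q1 × Q3), which is 3.44 with 1.41 and 3.10 with 1.14, against 3.68 printed.
- *Unstated correlation.* 1.481 × √(1 − 0.45²) = 1.323, which is an ANCOVA residual SD at a baseline correlation of 0.45.

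A plain miscalculation is the third possibility.

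**Step 4: consequence under each reading (10 per group, two-sided 0.05).**

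| Reading | Effective SD | Power at 83% | Reduction detectable with 80% power |
|---|---|---|---|
| Quartiles right, no correlation credited | 1.481 | 71.6% | 86.0% |
| Quartiles right, correlation 0.45 | 1.323 | 80.8% | 82.7% |
| Quartiles right, correlation 0.5 | 1.283 | about 83% | 81.7% |
| Q1 is 1.41 | 1.32 | 80.8% | 82.7% |

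With the quartiles as printed, a correlation of about 0.43 is enough to restore 80% power at 83% (0.437 if the ANCOVA's 17 degrees of freedom are used).

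**The case against.** The best counter-argument is that the plan never says the SD comes from the quartile ratio alone. It gives three values, and they cannot all lie on one lognormal curve, since the geometric midpoint of the quartiles is 3.10 and the printed median is 3.68. Any single SD is then a compromise; reasonable choices run from 1.225 to 1.737, and 1.323 lies inside that range. An ordinary least-squares fit of lognormal quantiles to the three values on the mg/L scale gives 1.326 and a fitted lower quartile of 1.413. On that route the power claim survives with no misprint and no hidden correlation, and the agreement at 1.41 is weaker evidence of transposed digits. The stakes are also small: 83% and 86% are both very large effects, the outcomes are exploratory, and ANCOVA with a moderate baseline correlation would recover the power.

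Part of this stands. The printed values are not exactly lognormal, the misprint is only a possibility, and the consequence is limited. But the mg/L-scale fit is an unusual method that the plan does not mention. It gives 1.326 at the printed values and reaches only 1.3233 at the extreme of rounding, so it comes close to 1.323 without reproducing it. The plan chose the lognormal assumption, and the standard calculation under it gives 1.48 with or without the median. If the authors used another route, showing it would settle the matter.

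**Conclusion.** The concern holds and is minor. The printed quartiles and the stated SD do not agree under the plan's own assumption (1.48 against 1.323), and the claim of at least 80% power for an 83% reduction does not follow from the printed inputs. In the least favourable of the readings set out above, with quartiles correct and no correlation credited, power is about 72% rather than 80%, and the detectable reduction is 86%. Under the other readings the claim is essentially right. These figures rest on a two-sample comparison of log hsCRP with 10 per group and equal SDs. That the two numbers disagree is certain; which one is wrong cannot be settled from the documents.

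The paragraph on the interleukins and TNF-α openly assumes the same SD and is not an error in itself. The documents give no dispersion data for those markers, so their power cannot be checked.

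**What to change.** Check the hsCRP quartiles against their source and add a line showing how 1.323 was obtained. Then:

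- If 1.14 and 8.41 are right and no correlation was intended, replace 1.323 by 1.48 and give the detectable reduction as 86%, or keep 83% and state power of about 72%.
- If a baseline correlation was intended, state it, as is done for FMD and 6MWT. About 0.45 reproduces 1.323 and 83%; at 0.5 the detectable reduction is about 82%.
- If a quartile is misprinted, correct it and keep 1.323 and 83%.
- If another fitting method was used, name it and give the value it returns.

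If the SD changes and the value for the interleukins and TNF-α was taken from hsCRP, change it there too. The cost is one source check and rewording one or two power sentences. Sample size, design, planned analysis and primary power stay as they are.
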